Table 13-3 Classifications for Study Drug Action Taken With Regard to an AE61

Table 13-4 Classifications for Outcome of an AE62

[figure not shown]
[figure not shown]
List of Figures

Figure 2-1 VX18-121-101 Study Design for Part 1 (F/MF Genotypes).....5

Figure 2-2 VX18-121-101 Study Design for Part 2 (F/F Genotype).....5

Figure 9-1 VX18-121-101 Study Design for Part 1 (F/MF Genotypes).....28

Figure 9-2 VX18-121-101 Study Design for Part 2 (F/F Genotype).....29

List of Abbreviations

Abbreviation	Definition
AE	adverse event
ALP	alkaline phosphatase
ALT	alanine transaminase
AST	aspartate transaminase
AUC	area under the concentration versus time curve
AUC _{0-24h}	AUC from the time of dosing to 24 hours
β-hCG	beta-human chorionic gonadotropin
BMI	body mass index
CD	compact disc
CF	cystic fibrosis
CFQ-R	CF Questionnaire-Revised
CFTR	CF transmembrane conductance regulator gene
CFTR	CF transmembrane conductance regulator protein
CI	confidence interval
CMC	chemistry, manufacturing, and controls
CPAP	clinical pharmacology analysis plan
CRF	case report form
CRO	clinical research organization
CSR	clinical study report
CTCAE	Common Terminology Criteria for Adverse Events
C _{trough}	predose concentration
CYP	cytochrome P450
█	█
ECG	electrocardiogram
EDC	electronic data capture
EENT	eyes, ears, nose, and throat
ETT	Early Termination of Treatment
F508del	CFTR gene mutation with an in-frame deletion of a phenylalanine codon corresponding to position 508 of the wild-type protein
F508del	CFTR protein lacking the phenylalanine normally found at position 508 of the wild-type protein
FAS	Full Analysis Set
FDA	Food and Drug Administration
FDC	fixed-dose combination
█	█
FEV ₁	forced expiratory volume in 1 second
F/F	F508del/F508del
F/MF	F508del /minimal function
FSH	follicle-stimulating hormone
█	█
GCP	Good Clinical Practice
GGT	gamma-glutamyl transferase
GI	gastrointestinal
GLI	Global Lung Function Initiative

Abbreviation	Definition
GPP	Good Publication Practices
GPS	Global Patient Safety
HBE	human bronchial epithelial (cells)
HIPAA	Health Insurance Portability and Accountability Act
HR	heart rate
ICF	informed consent form
ICH	International Council for Harmonization
ICMJE	International Committee of Medical Journal Editors
IDMC	independent data monitoring committee
IEC	independent ethics committee
IPD	important protocol deviation
IRB	institutional review board
█	█
IVA	ivacaftor
IWRS	interactive web response system
LS	least squares
LUM	lumacaftor
MedDRA	Medical Dictionary for Regulatory Activities
MF	minimal function
min	minimum value
MMRM	mixed-effects model for repeated measures
N	number of subjects
OATP	organic anion transporting polypeptide
P	probability
pbo	placebo
PD	pharmacodynamic, pharmacodynamics
PE	physical examination
PI	pancreatic insufficient
PK	pharmacokinetic, pharmacokinetics
ppFEV ₁	percent predicted forced expiratory volume in 1 second
PR	PR interval
PT	Preferred Term
q12h	every 12 hours
qd	daily
QRS	the portion of an ECG comprising the Q, R, and S waves, together representing ventricular depolarization
QT	QT interval
QTc	QT interval corrected
QTcF	QT interval corrected by Fridericia's formula
█	█
RR	interval from the onset of 1 QRS complex to the next
SAE	serious adverse event
SAP	statistical analysis plan
SD	standard deviation
SET	study execution team
SI	SI units (International System of Units)
SOC	System Organ Class

Abbreviation	Definition
SUSAR	suspected, unexpected, serious adverse reaction
SwCl	sweat chloride
TC	triple combination
TE	treatment-emergent
TEAE	treatment-emergent adverse event
TEZ	tezacaftor
ULN	upper limit of normal
UV	ultraviolet
WHO-DD	World Health Organization-Drug Dictionary

5 INTRODUCTION

5.1 Background

Cystic fibrosis (CF) is an autosomal recessive, chronic disease with serious morbidities and frequent premature mortality. At present, there is no cure. CF affects more than 70,000 individuals worldwide.¹ Based on its prevalence, CF qualifies as an orphan disease.^{2,3}

CF is caused by reduced quantity and/or function of the CFTR protein due to mutations in the *CFTR* gene. The CFTR protein is an epithelial chloride channel that aids in regulating salt and water absorption and secretion and pH balance in sweat glands and multiple organs, including the lungs, pancreas, and other gastrointestinal (GI) organs. Despite progress in the treatment of CF with antibiotics and mucolytics, the predicted median age of survival for a person with CF is approximately 40 years.^{4,5} Progressive loss of lung function is the leading cause of mortality.⁶

There are more than 2000 variants described in the *CFTR* gene. The most commonly seen variants that are clearly associated with CF have been identified (336 to date), but many rare cases remain uncharacterized.⁷

Based on the understanding of the molecular defects caused by these *CFTR* mutations, 2 complementary approaches have been developed to address the decreased quantity and/or function of CFTR in order to enhance chloride transport in patients with CF. Correctors facilitate the cellular processing and trafficking to increase the quantity of CFTR at the cell surface. Potentiators increase the channel-open probability of the CFTR protein delivered to the cell surface to enhance ion transport. Depending on the *CFTR* genotype of the patient, both approaches may be required to ameliorate lung disease in patients with CF.

The therapeutic activity of CFTR correctors and potentiators has been established with products developed by Vertex Pharmaceuticals Incorporated and approved for the treatment of CF in patients with specific *CFTR* genotypes: ivacaftor (IVA) monotherapy (Kalydeco[®]), lumacaftor (LUM) in combination with IVA (Orkambi[®]), and tezacaftor (TEZ) in combination with IVA (Symdeko[™]/ Symkevi[®]). TEZ and LUM are first-generation CFTR correctors that improve the processing and trafficking of mutated CFTR protein, resulting in an increase in the quantity of protein at the cell surface. IVA increases the open-channel probability of the mutated CFTR protein that has been delivered to the cell surface, thereby enhancing total chloride transport. VX-561 (formerly known as CTP-656) is a deuterated isotope of IVA with a specific pattern of 9 substituted deuteriums. In vitro data indicate similar potency of VX-561 in human bronchial epithelial (HBE) cells relative to IVA. Safety pharmacology and nonclinical toxicology studies of VX-561 demonstrate a similar safety profile relative to IVA. Phase 1 clinical studies in healthy subjects have shown that VX-561 had a reduced rate of clearance, increased exposure, greater plasma levels at 24 hours, and a longer half-life compared to IVA, thereby supporting once daily dosing (refer to VX-561 Investigator's Brochure).

VX-121 is a next-generation CFTR corrector. In vitro, VX-121 also improves the processing and trafficking of mutated CFTR, thereby increasing the quantity of functional protein at the cell surface. The effect of VX-121 was additive to the effect of TEZ. The CFTR protein delivered to the cell surface by VX-121 alone or in combination with TEZ (VX-121/TEZ) was potentiated by IVA. In HBE cells derived from people homozygous for *F508del* and people heterozygous for *F508del* and a minimal function (MF) *CFTR* mutation (F/MF-HBE cells) and studied in vitro,

the triple combination (TC) of VX-121, TEZ, and IVA (VX-121/TEZ/IVA) increased CFTR chloride transport more than the dual combination of VX-121 and either TEZ or IVA under most conditions studied (refer to VX-121 Investigator's Brochure).

5.2 Study Rationale

This is the second clinical study of VX-121 and Part 1 is designed to evaluate the safety and efficacy of VX-121 in TC with TEZ/VX-561 in subjects with CF who are heterozygous for *F508del* and a MF *CFTR* mutation (F/MF genotypes). Conducting the study in subjects with these genotypes investigates the effect of treating 1 responsive allele (*F508del*). Additionally, the safety and efficacy of VX-121 in TC with TEZ/VX-561 will be evaluated in subjects with CF who are homozygous for *F508del* (F/F genotype) in Part 2, [REDACTED] if the sponsor chooses to conduct these optional parts of the study based on overall development goals for the program and results from other studies.

6 STUDY OBJECTIVES

6.1 Primary Objectives

Parts 1 (Subjects with F/MF genotypes) and 2 (Optional; Subjects with the F/F genotype)

- To evaluate the safety and tolerability of VX-121 in TC with TEZ/VX-561 (deuterated IVA)
 - To evaluate the efficacy of VX-121 in TC with TEZ/VX-561
- [REDACTED]

6.2 Secondary Objectives

Parts 1 and 2

- To evaluate the pharmacodynamic (PD) effect of VX-121 in TC with TEZ/VX-561
 - To evaluate the pharmacokinetics (PK) of VX-121 when administered in TC with TEZ/VX-561
 - To evaluate the PK of TEZ, VX-561, and their respective metabolites when administered in TC with VX-121
- [REDACTED]

7 STUDY ENDPOINTS

7.1 Primary Endpoints

- Safety and tolerability, based on the assessment of adverse events (AEs), laboratory test results, standard 12-lead ECGs, vital signs, and spirometry
- Absolute change in percent predicted forced expiratory volume in 1 second (ppFEV₁) from baseline through Day 29

7.2 Secondary Endpoints

- Absolute change in sweat chloride concentrations from baseline through Day 29
- Absolute change in Cystic Fibrosis Questionnaire-Revised (CFQ-R) respiratory domain score from baseline at Day 29
- PK parameters of VX-121, TEZ, VX-561, [REDACTED] and relevant metabolites

8 STUDY POPULATION

Eligibility will be reviewed and documented by an appropriately qualified member of the investigator's team before subjects are enrolled.

Subjects who meet all of the inclusion criteria and none of the exclusion criteria will be eligible.

8.1 Inclusion Criteria

1. Subject will sign and date an informed consent form (ICF).
2. Willing and able to comply with scheduled visits, treatment plan, study restrictions, laboratory tests, contraceptive guidelines, and other study procedures.
3. Subjects (male and female) aged 18 years or older on the date of informed consent.
4. Female subjects must have a negative serum pregnancy test at the Screening Visit.
5. Body weight ≥ 35 kg.
6. Subjects must be able to produce a valid (quantity-sufficient) sweat sample at screening. If the initial screening collection results in insufficient sweat volume, then the sweat chloride collection may be repeated once.

Subjects must have a sweat chloride value ≥ 60 mmol/L at screening or documented in the form of a laboratory report in the subject's medical record.

7. Confirmed diagnosis of CF as determined by the investigator.
8. Subjects must have an eligible *CFTR* genotype as noted below. If the screening *CFTR* genotype result is not received before the Run-in Period (Part 2) or randomization (Parts 1 [REDACTED] a previous *CFTR* genotype laboratory report may be used to establish

eligibility. Subjects who have been enrolled and whose screening genotype does not confirm study eligibility must be discontinued from the study (Section 9.9).

- Parts 1 [REDACTED] Heterozygous for *F508del* with a second *CFTR* allele carrying a mutation that does not produce a protein, or produces a protein that is not responsive to TEZ, IVA, or TEZ/IVA therapy (Appendix A)
 - Part 2: Homozygous for *F508del*
9. Subjects must have a forced expiratory volume in 1 second (FEV₁) $\geq 40\%$ and $\leq 90\%$ of predicted normal for age, sex, and height (equations of the Global Lung Function Initiative [GLI])⁸ at the Screening Visit. Spirometry measurements must meet American Thoracic Society/European Respiratory Society criteria⁹ for acceptability and repeatability.
 10. Stable CF disease as judged by the investigator.
 11. Willing to remain on a stable CF treatment regimen (other than protocol-specified changes in CFTR modulator regimen) through the Safety Follow-up Visit (Section 9.5).

8.2 Exclusion Criteria

1. History of any comorbidity that, in the opinion of the investigator, might confound the results of the study or pose an additional risk in administering study drug to the subject.
2. History of clinically significant cirrhosis with or without portal hypertension.
3. Risk factors for Torsade de Pointes and other ventricular arrhythmias, including but not limited to, history of any of the following: familial long QT syndrome, chronic hypokalemia, heart failure, left ventricular hypertrophy, chronic bradycardia, myocardial infarction, cardiomyopathy, history of arrhythmia (ventricular or atrial fibrillation), obesity, acute neurologic events (subarachnoid hemorrhage, intracranial hemorrhage, cerebrovascular accident, or intracranial trauma), or autonomic neuropathy.
4. Any of the following abnormal laboratory values at screening:
 - Hemoglobin < 10 g/dL
 - Total bilirubin $\geq 2 \times$ upper limit of normal (ULN)
 - Aspartate transaminase (AST), alanine transaminase (ALT), gamma-glutamyl transferase (GGT), or alkaline phosphatase (ALP) $\geq 3 \times$ ULN
 - Abnormal renal function defined as glomerular filtration rate ≤ 50 mL/min/1.73 m² (calculated by the Modification of Diet in Renal Disease Study Equation)^{10,11} for subjects ≥ 18 years of age
5. An acute upper or lower respiratory infection, pulmonary exacerbation, or changes in therapy (including antibiotics) for sinopulmonary disease within 28 days before the first dose of TEZ/IVA in the Run-in Period (Part 2) or the first dose of study drug in the Treatment Period (Parts 1 [REDACTED]).

6. Lung infection with organisms associated with a more rapid decline in pulmonary status (e.g., *Burkholderia cenocepacia*, *Burkholderia dolosa*, and *Mycobacterium abscessus*). For subjects who have had a history of a positive culture, the investigator will apply the following criteria to establish whether the subject is free of infection with such organisms:
 - The subject has not had a respiratory tract culture positive for these organisms within the 12 months before the date of informed consent.
 - The subject has had at least 2 respiratory tract cultures negative for such organisms within the 12 months before the date of informed consent, with the first and last of these separated by at least 3 months, and the most recent 1 within the 6 months before the date of informed consent.
7. An acute illness not related to CF (e.g., gastroenteritis) within 14 days before the first dose of TEZ/IVA in the Run-in Period (Part 2) or the first dose of study drug in the Treatment Period (Parts 1 [REDACTED]).
8. Standard 12-lead ECG demonstrating QTcF >450 msec at screening. If QTcF exceeds 450 msec, the ECG will be repeated 2 more times, and the average of the 3 QTcF values will be used to determine the subject's eligibility.
9. History of solid organ or hematological transplantation.
10. History of alcohol or drug abuse in the past year, including, but not limited to, cannabis, cocaine, and opiates, as deemed by the investigator.
11. Ongoing or prior participation in a study of an investigational treatment with the exception of the following:
 - Ongoing or prior participation in an investigational study of a Vertex CFTR modulator. A washout period of 28 days must elapse before Day 1.
 - For prospective subjects with ongoing or prior participation in all other interventional studies, a washout period of 28 days or 5 terminal half-lives (whichever is longer) must elapse before screening. The duration of the elapsed time may be longer if required by local regulations.
 - Ongoing participation in a noninterventional study (including observational studies and studies requiring assessments without administration of study drug or assignment to other interventions) is permitted.
12. Use of prohibited medications as defined in [Table 9-1](#), within the specified window before the first dose of TEZ/IVA in the Run-in Period (Part 2) or the first dose of study drug in the Treatment Period (Parts 1 [REDACTED]).

13. Subject, or close relative of the subject, is the investigator or a subinvestigator, research assistant, pharmacist, study coordinator, or other staff directly involved with the conduct of the study at that site. However, an adult (aged 18 years or older) who is a relative of a study staff member may be enrolled in the study provided that
- the adult lives independently of and does not reside with the study staff member, and
 - the adult participates in the study at a site other than the site at which the family member is employed.
14. Pregnant or nursing female subjects.

9 STUDY IMPLEMENTATION

9.1 Study Design

This is a Phase 2, [REDACTED] proof-of-concept study of VX-121. Study parts may be conducted in parallel or sequentially.

A schematic of the study design for Part 1 is shown in Figure 9-1, which has a randomized, double-blind, placebo-controlled, parallel-group design and evaluates VX-121 in TC with TEZ/VX-561.

Figure 9-1 VX18-121-101 Study Design for Part 1 (F/MF Genotypes)

	Treatment Period ^{a,b} (4 weeks)	Washout Period ^{b,c} (18 ± 3 days)	
Screening Period (4 weeks)	TC-20 mg (VX-121/TEZ/VX-561) N = 18	TEZ/ VX-561	Safety Follow-up Period (4 weeks)
	TC-10 mg (VX-121/TEZ/VX-561) N = 18		
	TC-5 mg ^d (VX-121/TEZ/VX-561) N = 9		
	Triple Pbo N = 9		
		Dual Pbo	

FDC: fixed-dose combination; F/MF: *F508del*/minimal function; N: number of subjects; pbo: placebo; PD: pharmacodynamic; PK: pharmacokinetic; ppFEV₁: percent predicted forced expiratory volume in 1 second; qd: daily; TC: triple combination; TEZ: tezacaftor

Note: Randomization will be stratified by ppFEV₁.

- ^a The planned VX-121 doses of 5 mg, 10 mg, and 20 mg qd may be adjusted based on emerging data from subjects with CF in Part D of Study VX17-121-001 (Study 001). However, no more than 3 dose levels of VX-121 will be evaluated, and the highest dose will not exceed 20 mg qd.
- ^b The dosage of TEZ and VX-561 will be TEZ 100 mg qd and VX-561 150 mg qd.
- ^c The Washout Period (18 ± 3 days) is included to enable a more thorough evaluation of VX-121 exposure-response relationships by conducting PK and PD assessments during the VX-121 washout.
- ^d TC-5 mg is optional.

A schematic of the study design for Part 2 is shown in Figure 9-2, which has a randomized, double-blind, TEZ/IVA-controlled, parallel-group design and evaluates VX-121 in TC with TEZ/VX-561. Part 2 is an optional part of the study, which will be conducted at the sponsor’s discretion.

Figure 9-2 VX18-121-101 Study Design for Part 2 (F/F Genotype)

	Run-in Period ^{a,b} (4 weeks)	Treatment Period ^{b,c} (4 weeks)	Washout Period ^{b,d} (4 weeks)	
Screening Period (4 weeks)	TEZ/IVA	TC-20 mg (VX-121/TEZ/VX-561) N = 18	TEZ/IVA	Safety Follow-up Period (4 weeks)
		Pbo + TEZ/IVA N = 9		

FDC: fixed-dose combination; F/F: *F508del/F508del*; IVA: ivacaftor; N: number of subjects; pbo: placebo; PD: pharmacodynamic; ppFEV₁: percent predicted forced expiratory volume in 1 second; q12h: every 12 hours; qd: daily; TC: triple combination; TEZ: tezacaftor

Note: Randomization will be stratified by ppFEV₁.

- ^a All subjects are required to complete the TEZ/IVA Run-in Period to establish a reliable on-treatment (TEZ/IVA) baseline.
- ^b The dosage of TEZ/IVA will be TEZ 100 mg qd/IVA 150 mg q12h, which will be administered as TEZ 100 mg/IVA 150 mg FDC in the morning and IVA 150 mg in the evening.
- ^c Part 2 will evaluate the same VX-121 dose (20 mg qd) used in Part 1. This dose may be adjusted downward based on emerging data from Part D of Study 001. The dosage of TEZ and VX-561 will be TEZ 100 mg qd and VX-561 150 mg qd.
- ^d The 4-week Washout Period is included to evaluate the effect on PD and efficacy endpoints as subjects step down from TC to TEZ/IVA, after the VX-121 washout.

9.1.1 Screening

Screening Visit assessments are shown in [Table 3-1](#), [Table 3-2](#), [REDACTED]

The Screening Period will occur within 28 days before the first dose of study drug. The site investigator (or designee) will confirm and document study eligibility before randomization.

9.1.1.1 Repetition of Screening Assessment(s)

Screening assessments may be repeated once to establish study eligibility. If repeat values of the individual assessment(s) are within the eligibility criteria and completed within the screening window, then the subject is eligible for the study.

9.1.1.2 Rescreening

Subjects may be rescreened only once. If a subject is rescreened, all screening assessments will be repeated except for *CFTR* genotyping, follicle-stimulating hormone (FSH) level (if serum FSH level was ≥ 40 mIU/mL during prior screening), and sweat chloride level. If a subject is rescreened, the new screening window will begin once the first rescreening assessment has been initiated.

9.1.1.3 Extension of Screening Period Window

The Screening Period window may be extended by 2 weeks for the following reasons:

- Repetition of the Screening Period assessments (Section 9.1.1.1)

- Unexpected operational or logistic delays, or to meet the eligibility criteria
- Repetition of spirometry assessment if results are of poor quality

9.1.2 TEZ/IVA Run-in Period (Part 2)

The TEZ/IVA Run-in Period of Part 2 is 4 weeks. Subjects will be evaluated as outpatients.

Study visits during the Run-in Period will occur as shown in [Table 3-2](#). Study drug administration details are provided in [Section 9.6](#).

On the Day -14 Visit, spirometry and sweat chloride will be assessed. The Day -14 Visit spirometry assessment will be used for stratification of randomization ([Section 9.2](#)).

Study eligibility will be confirmed before the first dose of TEZ/IVA in the Run-in Period (on the Day -28 Visit). Subjects who prematurely discontinue TEZ/IVA during the Run-in Period will not be randomized or participate in the Treatment Period, unless they rescreen and complete another 4-week Run-in Period ([Section 9.1.1.2](#)).

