Vital signs ^l	X	X		X	X	X	X	X	X	X	X
Pulse oximetry ^l	X	X		X	X	X	X	X	X	X	X
Physical examination ^m	Complete	Abbrev.		Abbrev.	Abbrev.	Abbrev.	Abbrev.		Abbrev.	Complete	Complete
Standard 12-lead ECG ⁿ	X	X		X	X	X	X	X	X	X	X
Sweat chloride ^o	X		X	X		X	X	X ^p	X ^p	X	
Spirometry ^q	X		X ^r	X	X	X	X	X ^p	X ^p	X	X

^a All assessments will be performed before dosing, unless noted otherwise. Assessments that are collected before and after dosing will only be collected once if study drug is not administered on the day of the visit (i.e., premature discontinuation of study drug treatment).

^b All screening results must be reviewed before the Run-in Period.

^c To qualify to continue into the Treatment Period, conditions for entry must be satisfied (Section 9.1.3).

^d If the subject prematurely discontinues study drug, an ETT Visit should be scheduled as soon as possible after the decision to terminate study drug treatment (Section 9.1.6). A final PK sample will be drawn from subjects who discontinue study drug for any reason (except withdrawal of consent). Safety assessments may also be performed at the discretion of the investigator.

^e Part 2 subjects who meet criteria specified in Section 9.1.5 will not have a Safety Follow-up Visit.

^f Study drug refers to VX-121, TEZ, VX-561, TEZ/IVA, IVA, and matching placebos.

^g Assessments at this visit may be performed postdose.

^h Randomization may occur on the previous day (Day -1) after all conditions for entering the Treatment Period have been confirmed (Section 9.1.3).

ⁱ The CFQ-R must be completed before any other assessments scheduled at relevant visits.

^j The predose assessment on Day 1 may be performed on the previous day (Day -1) if randomization has occurred.

^k Weight and height will be measured with shoes off.

^l Vital signs and pulse oximetry will be collected after the subject has been at rest for at least 5 minutes (Sections 11.6.3 and 11.6.4).

^m Complete and abbreviated PEs are described in Section 11.6.3.

ⁿ Standard 12-lead ECGs will be performed in the supine position after the subject has been at rest for at least 5 minutes (Section 11.6.5). The ECG will be done before any other procedures that may affect heart rate, such as blood draws. ECGs collected on Day 1 before dosing will be performed in triplicate.

^o See Section 8.1 for information about the sweat chloride assessment for study eligibility.

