9.3 Rationale for Study Elements

9.3.1 Study Design

Parts 1 [REDACTED]

Parts 1 [REDACTED] will evaluate the safety, tolerability, PK, PD, and efficacy of VX-121 administered in TC with TEZ/VX-561 (Part 1) [REDACTED] in subjects with CF with F/MF genotypes.

Efficacy has not been established for a corrector, potentiator, or any corrector/potentiator combination in subjects with F/MF genotypes. Because there is no effective treatment for this population, a placebo arm will be included as the control treatment to assess whether any observed effects are treatment-related or simply related to the study conditions.

The Washout Period (18 ± 3 days; Section 9.1.4) is included to enable a more thorough evaluation of VX-121 exposure-response relationships by conducting PK and PD assessments during the VX-121 washout.

Part 2

Part 2 will evaluate the safety, tolerability, PK, PD, and efficacy of VX-121 in TC with TEZ/VX-561 in subjects with CF with the F/F genotype, if the sponsor chooses to conduct this optional part of the study.

The efficacy and safety of TEZ/IVA in F/F subjects have been demonstrated in Study VX14-661-106 (Study 661-106).¹² Therefore, placebo/TEZ/IVA has been chosen as the control treatment to assess whether any observed effects are treatment-related or simply related to the study conditions.

A 4-week TEZ/IVA Run-in Period (Section 9.1.2) is included to establish a reliable on-treatment (TEZ/IVA) baseline for the Treatment Period.

The 4-week Washout Period (Section 9.1.4) is included to evaluate the effect on PD and efficacy endpoints as subjects step down from TC to TEZ/IVA, after the VX-121 washout.

Parts 1, 2, [REDACTED]

The extent of response to CFTR modulator treatment may depend on the subject's ppFEV₁ value (an index of disease severity) before the start of TC study drug dosing. Some subjects in Part 2 (subjects with the F/F genotype) may be receiving treatment with LUM/IVA or TEZ/IVA at screening, while some subjects may not be receiving treatment with CFTR modulators. It is unlikely that subjects enrolling in Parts 1 [REDACTED] (subjects with F/MF genotypes) are receiving LUM/IVA or TEZ/IVA at screening, as the benefit of these drugs has not been established in patients with F/MF genotypes. Therefore, randomization will be stratified by the ppFEV₁ value determined during screening for Parts 1 [REDACTED] and during the TEZ/IVA Run-in Period, after at least 13 days of TEZ/IVA (Day -14 assessment), in Part 2.

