- The TE period for the Treatment Period will include the time from the first dose of study drug in the Treatment Period to 28 days after the last dose of study drug (from treatment period or washout period) or the completion date of study participation (obtained from the end of follow-up page of the CRF), whichever occurs first.

**Baseline value**, unless otherwise specified, will be defined as the most recent non-missing measurement (scheduled or unscheduled) collected before the first dose of study drug in the Treatment Period. For ECG, baseline will be defined as the most recent non-missing measurement (or the average of triplicate measurements, if the most recent non-missing measurement is obtained in triplicate), before the first dose of study drug in the Treatment Period.

**Absolute change** from baseline will be calculated as postbaseline value – baseline value.

**Relative change** from baseline will be calculated as (postbaseline value – baseline value)/baseline value.

**Unscheduled visits:** Unscheduled visit measurements will be included in analysis as follows:

- In scheduled visit windows per specified visit windowing rules
- In the derivation of baseline
- In the derivation of maximum and minimum values during TE period, and maximum and minimum change from baseline values for safety analyses
- In individual subject data listings as appropriate

**Visit windowing rules:** The analysis visit windows for protocol-defined visits are provided in [Appendix A](#).

Spirometry (ppFEV1) will be used for both efficacy and safety purposes. For efficacy analysis, the assessments will follow the visit windowing rules for efficacy. For safety analysis, the nominal visits will be used for ppFEV1 collected at both pre-dose on Day 1 and pre-dose on Day 2 (for Part 1 only).

**Incomplete/missing data** will not be imputed, unless specified otherwise.

**Outliers:** No formal statistical analyses will be performed to detect or remedy the presence of statistical outliers.

**Multiplicity:** There will be no multiplicity adjustment for performing multiple hypothesis tests.

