##### **8.3.1.2 Primary Analysis for Parts 1, 2, [REDACTED]**

The null hypothesis to be tested is that the mean absolute within-group change from baseline in ppFEV1 through Day 29 is zero for VX-121 in triple combination (TC) with TEZ/VX-561 in Parts 1 and 2, [REDACTED] separately. A 2-sided *p*-value of 0.05 or less will be interpreted as sufficient evidence to reject the null hypothesis.

The primary analysis will be performed using a mixed-effects model for repeated measures (MMRM) with change from baseline in ppFEV1 at Day 15 and Day 29 as the dependent variable for each part, separately. The model will include treatment group, visit, and treatment-by-visit interaction as fixed effects and subject as a random effect, with the continuous baseline ppFEV1 as a covariate. For Part 1 the model will include 4 treatment groups: placebo, TC-5 mg, TC-10 mg, TC-20 mg. For Part 2, the model will include 2 treatment groups: placebo + TEZ/IVA, and TC-20 mg. [REDACTED]

[REDACTED] The model will be estimated using restricted maximum likelihood. Denominator degrees of freedom for the F test for fixed effects will be estimated using the Kenward-Roger approximation. An unstructured covariance structure will be used to model the within-subject errors. If the model estimation does not converge, a compound symmetry covariance structure will be used instead.

Conditional on the observed data and covariates, missing ppFEV1 data will be assumed to be missing at random; consequently, no imputation of missing data will be performed.

The adjusted means and 95% confidence intervals (CI) of the average treatment effect through Day 29 (average over Day 15 and Day 29 only) will be presented for all within-treatment and between-treatment comparisons, for each part. A 2-sided *p*-value will be provided for within-treatment comparisons.

Further, the adjusted mean and corresponding 95% CI for each treatment group and the treatment difference between each triple combination and placebo or TEZ/IVA at Day 15 and Day 29 will be provided, for each part. A 2-sided p-value will be provided for within-treatment comparisons.

The adjusted mean (with SE) obtained from the MMRM analysis at Day 15 and Day 29 will be plotted by treatment group, for each part.

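### Part 2 takes on-TEZ/IVA readings of ppFEV1 and sweat chloride at both Day -14 and Day 1, but the model uses only Day 1: a modest, avoidable loss of precision in the between-arm comparison

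*Protocol*

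**What the plan says.** Protocol 9.1 (Figure 9-2, footnote a) gives the purpose of the Part 2 run-in: "All subjects are required to complete the TEZ/IVA Run-in Period to establish a reliable on-treatment (TEZ/IVA) baseline". Section 9.1.2 and Table 3-2 schedule spirometry and sweat chloride at Day -14 for all Part 2 subjects: "On the Day -14 Visit, spirometry and sweat chloride will be assessed. The Day -14 Visit spirometry assessment will be used for stratification". Section 9.3.1 places this reading "after at least 13 days of TEZ/IVA (Day -14 assessment), in Part 2". Both measures are scheduled again at Day 1.

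Stratification is the only stated use of the Day -14 spirometry. Protocol 9.2 sets the cut at 70 and provides a fallback when the Day -14 value is invalid or unavailable.

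SAP 8.1 says that baseline "will be defined as the most recent non-missing measurement (scheduled or unscheduled) collected before the first dose of study drug in the Treatment Period", and protocol 12.3.1 has the same rule. SAP 8.3.1.2 fits treatment, visit and their interaction, "with the continuous baseline ppFEV 1 as a covariate". No stratum term or Day -14 value is listed. SAP 8.3.2.2.1 uses a similar model for sweat chloride, and SAP 8.3.1.4 plans no sensitivity analysis.

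**The concern.** Each Part 2 subject is scheduled to give two on-TEZ/IVA readings before randomised treatment, and the analysis uses one. The visit-to-visit error of the Day 1 reading enters every subject's change. Covariate adjustment for that same reading does not remove the error. The plan averages Days 15 and 29 after baseline but does nothing comparable before it. The Day -14 ppFEV1 determines the randomisation stratum, yet it does not appear in the model.

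The Day -14 sweat chloride has no stated analysis use in the protocol or SAP, except by default if Day 1 is missing.

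Precision is at stake in a small part of the study (18 v 9), chiefly for the difference between TC-20 mg and TEZ/IVA. The stated power covers only within-group tests with 18 subjects.

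**Working it through.** **The plan's own figure.** Inputs from protocol 12.1: n = 18, mean change 7, SD of change 8. SAP 8.3.1.2 sets two-sided 0.05. The one-sample noncentrality is 7 / (8/√18) = 3.71 with 17 df, which gives power of 93.8%. The claim of at least 90% holds with the Day 1 baseline. The same test with the 9 control subjects has 63.5%.

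**Variance model.** Let s be the within-subject SD per visit and r the SD of true individual response. Read the SD of 8 as applying to the change averaged over Days 15 and 29:

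r² + s²/2 + s² = 64.

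The documents do not give s, so it is varied from 2 to 5. The between-subject SD is also not given and is assumed to be 14, so B = 196. Visit errors are taken as independent.

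**Residual variance after adjustment.** The averaged post-baseline value has variance B + 64 − s². Given k pre-treatment readings, the residual variance is

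(B + 64 − s²) − B²/(B + s²/k).

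At s = 4 and k = 1: 244 − 38416/212 = 62.79. With k = 2: 244 − 38416/204 = 55.69. Under this model, entering both readings as covariates leaves the same residual variance as adjusting for their mean.

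**SE of TC minus TEZ/IVA.** With p covariates and 27 subjects, the SE is √[residual × (1/18 + 1/9) × (1 + p/(24 − p))]. The last factor is the average price of estimating the slopes: 1 + 1/23 for one covariate and 1 + 2/22 for two.

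| s | Residual, Day 1 only | Residual, both readings | SE, Day 1 only | SE, Day -14 as second covariate | SE, averaged baseline |
|---|---|---|---|---|---|
| 2 | 63.92 | 61.98 | 3.33 | 3.36 (0.7% larger) | 3.28 (1.5% smaller) |
| 3 | 63.60 | 59.40 | 3.33 | 3.29 (1.2% smaller) | 3.21 (3.4% smaller) |
| 4 | 62.79 | 55.69 | 3.31 | 3.18 (3.7% smaller) | 3.11 (5.8% smaller) |
| 5 | 61.17 | 50.75 | 3.26 | 3.04 (6.9% smaller) | 2.97 (8.9% smaller) |

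Simulation of the 18 v 9 design gave about 0%, 2%, 4% and 6% for the covariate and 2%, 4%, 6% and 8% for averaging. The two agree to within about one percentage point.

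With the second covariate, the 95% half-width goes from 2.064 × 3.305 = 6.8 to 2.069 × 3.182 = 6.6 points at s = 4. At s = 5 it goes from 2.064 × 3.262 = 6.7 to 2.069 × 3.038 = 6.3.

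**Within-group mean, TC arm.** Averaging lowers the variance of the change from 64 to 64 − s²/2. At s = 4 the SD becomes √56 = 7.48, and the SE goes from 1.89 to 1.76 (6.5%). The second covariate does little here: about 1% at s = 4 in simulation.

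**Drift.** If the mean rises by x between Day -14 and Day 1, averaging shifts each within-group change by x/2 and leaves the between-arm contrast unbiased. In simulation a 2-point drift moved the averaged within-group mean by 1 point, while the covariate version moved neither estimate. The variance saved by averaging in 18 subjects is (s²/2)/18 = s²/36. The squared bias is x²/4. Averaging therefore has the larger mean squared error once x exceeds s/3, for example 1.3 points at s = 4.

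**Shared error.** If the two readings' errors correlate at ρ, the variance saved by averaging is s²(1 − ρ)/2. With an assumed ρ of 0.5 at s = 4, this is 4 of 64 (6%) instead of 8 of 64 (12.5%).

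**The case against.** The best counter-argument is that the two visits are not interchangeable. Table 3-2 says of Day -14: "Assessments at this visit may be performed postdose". Day 1 must be predose. The Day -14 window is +13 days, so a late visit may fall next to Day 1 and share its error. Protocol 9.5 aligns Day 1 to within 3 days of the start of an inhaled-antibiotic cycle, so for cycling subjects Day -14 falls at a different point of the cycle. Protocol 9.3.1 allows some subjects to enter without a modulator or on LUM/IVA, so drift during run-in is plausible. Section 9.3.2 says that improvement is seen by Day 15. It does not say that the response is complete by then, and it is silent on sweat chloride. All of this stands, and it is why Day 1 should remain the subtracted baseline.

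It is also true that SAP 8.3.1.2 gives P values only for within-treatment comparisons. Between-arm results are intervals, so the gain is best read as interval width, not power.

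Sweat chloride is already a mean of two arms at each visit (SAP 8.3.2.1), and no SD is given for it. No gain can be quantified there. A use for the Day -14 value in the separate Modeling and Simulation Plan cannot be excluded.

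These objections do not count against the covariate. A pre-randomisation reading entered as a covariate leaves both estimates unbiased under a common drift, whatever its timing. A poorly matched reading only reduces the gain.

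**Conclusion.** The point holds as a modest efficiency improvement. Part 2 collects a second on-treatment pre-randomisation reading and leaves it out of the model, including the ppFEV1 value on which randomisation was stratified. The second covariate would shorten the TC-minus-TEZ/IVA interval by a few percent at best: nothing at s = 2, about 4% in SE at s = 4 and 6 to 7% at s = 5. These figures rest on an SD of change of 8, an assumed between-subject SD of 14, independent visit errors and complete data. They shrink if a late Day -14 visit shares error with Day 1.

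A reader might go further and infer that the Day 1 baseline is unreliable, that Part 2 is underpowered as stated, or that the two-visit mean should replace Day 1 in the primary analysis. The documents support none of these. The baseline rule is valid and the same in both documents, the stated power is met, and averaging exposes the primary within-group change to a bias of half the run-in drift.

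**What to change.** Keep Day 1 as the subtracted baseline. In SAP 8.3.1.2 and 8.3.2.2.1, for Part 2 only, add the Day -14 reading of the same endpoint as a second continuous baseline covariate for the TC-minus-TEZ/IVA contrast. State a rule for a missing or invalid Day -14 value, for example substituting the Day 1 value.

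In SAP 8.3.1.4, and likewise for sweat chloride, prespecify a Part 2 sensitivity analysis that uses the mean of Day -14 and Day 1 as baseline. Report it with the mean Day -14 to Day 1 drift, so that the reader can see how much of any difference in the within-group change is half that drift.

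The cost is SAP wording and 1 degree of freedom, with no new visits or data. Expect little effect on the within-group result, and a slight loss of precision if s is near 2. Protocol 12.3.4.1 lists only baseline ppFEV1 as covariate, so the SAP should record the addition as a change from the protocol model.
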